11.5. Pharmacokinetic/Pharmacodynamic Analyses

Not applicable.

11.6. Safety Analyses

The safety analysis set will be used for all safety analyses. For safety endpoints, the data from AE assessments, clinical laboratory assessments, physical examinations, 12-lead ECGs, vital signs (including weight) assessments, the C-SSRS evaluation, and the PWC evaluations will be summarized. Preceding study and extension study data will be summarized separately and also may be combined.

11.6.1. Adverse Event Analyses

AEs will be tabulated using the Medical Dictionary for Regulatory Activities (MedDRA) classification system. A TEAE is defined as an AE that emerges during treatment (having been absent prior to treatment) or worsens relative to the pre-treatment state. For subjects who transfer directly into this study from a preceding study (DS5565-A-E309, DS5565-A-E310, DS5565-A-E311), an AE that started in the preceding study will not be considered treatment-emergent in this study unless the AE worsens in severity during this study. The frequency of subjects experiencing a specific TEAE will be tabulated by system organ class, preferred term, seriousness (see Section 9.3.2), worst severity (see Section 9.3.3), and relationship to study drug (see Section 9.3.4). AEs of special interest

(defined in the SAP) will be summarized separately. In the by-subject analysis, a subject having the same event more than once will be counted only once. Listings of deaths, SAEs, and AEs leading to treatment discontinuation of a subject will be presented.

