9. SAFETY ASSESSMENTS

9.1. Adverse Events

All clinical AEs (defined in Section 9.3) occurring after the subject has signed the ICF and up to 4 weeks after the last dose of study medication (i.e. the follow-up period), whether observed by the investigator or reported by the subject, will be recorded on the AE eCRF page. For subjects rolled over from a preceding study (DS5565-A-E309, DS5565-A-E310, or DS5565-A-E311), any AE that is ongoing at the start of this study will be recorded as an AE in this study, and all AEs (new or from a preceding study) will be followed until resolution. For these rolled-over subjects, all AEs will be evaluated in the context of their experience in the preceding study.

All laboratory, vital sign, or ECG values should be appraised by the investigator as to clinical significance. Isolated abnormal laboratory results, vital sign findings, or ECG findings should be reported as AEs if they are symptomatic, lead to study drug discontinuation, require corrective treatment, or are otherwise defined as an adverse event of special interest (AESI) [please refer to Section 9.2].

All SAEs are to be reported according to the procedures in Section 9.4 (SAE Reporting-Procedure for Investigators). Always report the diagnosis as the AE or SAE term. When a diagnosis is unavailable, report the primary sign or symptom as the AE or SAE term with additional details included in the SAE narrative until the diagnosis becomes available. If the signs and symptoms are distinct and do not suggest a common diagnosis, report as individual entries of AE or SAE. For events that are serious due to hospitalization, the reason for hospitalization must be reported as the SAE (diagnosis or symptom requiring hospitalization). Pre-planned (prior to signing the ICF) procedures or hospitalizations for pre-existing conditions which do not worsen in severity should not be reported as SAEs (see Section 9.3 for Definitions). For deaths, the underlying or immediate cause of death should always be reported as an SAE. In addition, any serious, untoward event that may occur subsequent to the reporting period that the Investigator assesses as related to study drug should also be reported and managed as an SAE.

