9.3.2. Serious Adverse Event (SAE)

An SAE is defined as any untoward medical occurrence that at any dose:

- Results in death
- Is life-threatening
- Requires inpatient hospitalization or prolongation of existing hospitalization
- Results in persistent or significant disability/incapacity
- Is a congenital anomaly/birth defect, or

- Is an important medical event

Note: The term “life-threatening” in the definition of “serious” refers to an event in which the subject was at risk of death at the time of the event; it does not refer to an event which hypothetically might have caused death if it were more severe (ICH E2A Guideline. Clinical Safety Data Management: Definitions and Standards for Expedited Reporting, Oct 1994).

Medical and scientific judgment should be exercised in deciding whether expedited reporting is appropriate in other situations, such as important medical events that may not be immediately life-threatening or result in death or hospitalization but may jeopardize the subject or may require intervention to prevent one of the other outcomes listed in the definition above. Examples include allergic bronchospasm, convulsions, and blood dyscrasias or development of drug dependency or drug abuse.

Note:

- A procedure is not an AE or SAE, but the reason for the procedure may be an AE or SAE.
- Pre-planned (prior to signing the ICF) surgeries or hospitalizations for pre-existing conditions which do not worsen in severity are not SAEs.

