9.3.3. Adverse Event Severity

The following definitions should be used to assess severity of AEs:

- Mild: Awareness of sign or symptom, but easily tolerated, i.e. does not interfere with subject’s usual function.
- Moderate: Discomfort enough to cause interference with usual activity.
- Severe: Incapacitating with inability to work or do usual activity i.e. interferes significantly with subject’s usual function.

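### A rollover subject's carried-over AE that turns serious or ends treatment without a rise in severity grade is missing from the TEAE incidence tables

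*Combined protocol and SAP*

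**What the plan says.** Section 11.6.1 first gives a general definition: a TEAE is an AE that is new on treatment "or worsens relative to the pre-treatment state". For subjects who transfer directly from E309, E310 or E311 it then sets a narrower test. An AE that began in the preceding study "will not be considered treatment-emergent in this study unless the AE worsens in severity during this study".

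The same section specifies the incidence tables, and they are confined to TEAEs: "The frequency of subjects experiencing a specific TEAE will be tabulated by system organ class, preferred term, seriousness", then by worst grade and by causality. Deaths, SAEs and AEs leading to discontinuation are to be listed. AEs of special interest get a separate summary, with their definition left to the SAP.

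Section 9.1 brings the earlier events into this study's database: for rollover subjects, "any AE that is ongoing at the start of this study will be recorded as an AE in this study".

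**The concern.** The rollover test looks at one attribute of an AE, its intensity grade. A long-term safety study also needs to know whether a persisting reaction put someone in hospital or ended treatment. Either can happen with no change of grade, and the planned tables would then not count the event.

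This matters because TEAEs are the first-named component of the primary endpoint (Section 3.1.3), and the study hypothesis concerns tolerability over as long as a year (Section 2.2). A database snapshot of this study may support registration (Section 11.8). Rollover subjects could be a large share of the study: Section 11.11 anticipates 2100 to 2500 completers of the double-blind studies, against a goal of about 500 subjects with at least 52 weeks of exposure. A reader who compares the serious-TEAE table with the SAE listing could find more events in the listing, with nothing in the plan to explain the difference.

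**Working it through.** No figure in the plan is at issue, so the check is one of definitions, followed by a search for any other output that would restore the events.

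**Step 1: does severity include seriousness here?** Section 9.3.3 opens "The following definitions should be used to assess severity of AEs" and gives three grades: mild, moderate and severe. The top one is "Severe: Incapacitating with inability to work or do usual activity". Section 9.3.2 opens "An SAE is defined as any untoward medical occurrence that at any dose" and lists outcome criteria, among them "Requires inpatient hospitalization or prolongation of existing hospitalization". Stopping drug is coded in a third place, the action-taken field of Section 9.3.5. Section 11.6.1 itself refers to 9.3.2 for seriousness and to 9.3.3 for severity. The word severity in the rollover rule therefore means the grade and nothing else.

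**Step 2: apply the rule to each kind of carried-over AE.**

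| Course in this study | TEAE? | In TEAE incidence tables? | Where else it appears |
|---|---|---|---|
| Grade rises, serious or not | Yes | Yes | Listings, if serious or leading to discontinuation |
| Grade unchanged, becomes serious | No | No | SAE listing |
| Grade unchanged, leads to discontinuation | No | No | Discontinuation listing; disposition count |
| Already severe on entry | Never, since no higher grade exists | No | Listings, if serious, fatal or leading to discontinuation |
| Grade unchanged, neither serious nor treatment-ending | No | No | This study's AE database; preceding-study summary |

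Rows two to four are the gap. Row five is what the rule is meant to do: it avoids counting an old, stable event as new.

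**Step 3: can a treatment-limiting AE keep its grade?** Yes. Under Section 5.1.1, down-titration or discontinuation at the higher dose turns on the occurrence of a clinically relevant AE, not on a rise in its grade. A persisting moderate event can meet that condition.

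**Step 4: does another planned output give the missing incidence?** Sections 11.3 and 4.2.1 count withdrawals with adverse event as a reason, but not by preferred term. The listings show individual cases, not rates. Section 11.6 summarizes preceding-study data separately and allows, without requiring, a combined summary. Sections 11.6.2, 11.6.6 and 11.6.7 summarize laboratory, C-SSRS and PWC data whatever the TEAE status, but these are not AE tables. None gives incidence by preferred term of SAEs, or of AEs leading to discontinuation, that occur in this study irrespective of treatment emergence.

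**The case against.** The strongest reply is that the route is narrow and the events stay visible. Much of this stands.

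- Severe means incapacitating, so a mild or moderate AE that comes to need hospitalization will often go up a grade as well, and is then counted.
- Section 9.1 requires the reason for a hospitalization and the cause of a death to be reported as the SAE. If that is a new diagnosis with onset in this study, it is a TEAE in its own right.
- Inclusion criterion 4 and exclusion criterion 1 keep out subjects with significant safety problems or unstable illness in the preceding study, so AEs already severe on entry should be few.
- The detailed SAP that Section 11.2 promises is not part of the text available for this review. It may already contain the missing tables, and its definition of AEs of special interest may capture some of these events.

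These points limit the number of events. They do not change how the rule classifies those that remain.

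Four stronger readings are tempting, and the documents do not support them.

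- *The events survive only in listings, or persistent ones appear in no table at all.* Disposition counts AE withdrawals, and the preceding study's own summary covers AEs that began there.
- *The rule makes rollover subjects look safer than de novo subjects.* De novo subjects' AEs are recorded from consent, and those present before treatment must also worsen to count. The rollover test is the narrower of the two, but nothing in the documents shows or sizes a resulting bias.
- *The missed fraction of serious events can be calculated.* No rate of AEs ongoing at rollover is given. The 500 in Section 11.11 counts subjects with at least 52 weeks of exposure, not everyone dosed, so it is not the denominator of the safety set either.
- *The date on which an AE became serious is already recorded.* Section 9.4.1 asks for dates of onset, treatment and resolution; a separate date of becoming serious is not mentioned.

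**Conclusion.** The point holds as a gap in tabulated incidence. As Section 11.6.1 is written, a carried-over AE that becomes serious or leads to discontinuation at an unchanged grade, or that entered as severe, is excluded from every TEAE incidence table. The serious-TEAE count may therefore fall short of the SAE listing. The number of subjects is probably small and cannot be estimated from the documents. The conclusion rests on two things: that severity means the grade of Section 9.3.3, which the section's own cross-references support, and that the separate SAP does not already add the tables. It is a worthwhile low-cost improvement to the primary safety reporting, not a flaw that undermines the study.

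**What to change.** Leave the TEAE definition alone. Letting a dose action or a discontinuation define emergence would mix action taken with onset, and doing so only for carried-over events would treat rollover and de novo subjects differently. Instead, add to Section 11.6.1 and the SAP:

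1. An incidence table by system organ class and preferred term of all SAEs on or after the first extension dose, regardless of treatment-emergent status, shown separately for rollover and de novo subjects.
2. The same table for all AEs leading to discontinuation.
3. One table, in rollover subjects, of AEs ongoing at Visit 4 by outcome: resolved, still ongoing at end of treatment, became serious, led to dose reduction or discontinuation. These rows can overlap, and the table should say so.

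The carried-over AEs (Section 9.1), action taken (9.3.5), outcome (9.3.6) and seriousness (9.4.1) are already collected, so no visit or procedure is added. Before programming, confirm that the eCRF or SAE report can place the time at which a carried-over AE became serious; if not, the SAP should state how an SAE is assigned to this study. The cost is a few extra tables and slightly higher reported counts.

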1.2. Study Rationale

DS-5565 is an oral analgesic drug being developed for chronic use in FM and other indications. This open-label extension study will provide important long-term safety data in subjects who will be dosed on DS-5565 for up to 1 year.

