4.2.3. Subject Replacement

Subjects removed from the study for any reason will not be replaced.

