11. STATISTICAL METHODS

11.1. Analysis Sets

The following analysis sets will be used to summarize the data from this study:

- The enrolled analysis set will include all subjects who signed the ICF and were enrolled into the study
- The safety analysis set will include all subjects who received at least 1 dose of study medication.

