11.2. General Statistical Considerations

The statistical package SAS[®] (Version 9.2 or higher) will be used to produce all summary tables and figures and data listings.

Raw data will be presented with the same precision with which they were collected.

For summary statistics, means and medians will be displayed to one more decimal place than was determined for raw data, dispersion statistics will have two more decimal places, and the minimum and maximum will be displayed to the same number of decimal places as the raw data.

Quantitative data will be tabulated with descriptive summary statistics: arithmetic mean, standard deviation, median, minimum and maximum values, and number of observations. For categorical data, frequency tables will be provided.

For variables expressed as percent, the denominators for the calculation of percentage will be the number of subjects who had that variable assessed.

A detailed SAP describing the methodology to be used in the final analysis will be prepared before data unblinding. A change in the planned statistical analysis will require a protocol amendment only if it substantively alters the principal features of the protocol. Any deviations from the planned statistical analyses in the protocol will be fully described in the SAP.

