11.8. Interim Analyses

The sponsor expects that approximately 500 subjects across the development program for DS-5565 will need to be exposed to DS-5565 for at least 52 weeks to support registration. If this open-label extension study (DS5565-A-E312) is still ongoing when the above condition is met, the sponsor intends to take a snapshot of the database of this open-label extension study to support registration. The totality of the study data for DS-5565-A-E312 will be analyzed at the conclusion of the study.

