11.11. Sample Size Determination

Subjects who complete the double-blind studies are eligible to rollover to this open-label extension study. Although it's unknown how many subjects will complete the double-blind studies, the number is anticipated to be between 2100 and 2500. In addition subjects who did not participate in a preceding double-blind study (referred to as de novo subjects) may be enrolled. Overall, the goal of the open-label extension study is to collect long-term safety data on approximately 500 subjects exposed to DS-5565 for at least 52 weeks. During the conduct of the open-label study, subject withdrawal rates will be closely monitored. Entry into the open-label study will be stopped when the sponsor anticipates that the desired number of subjects completing 52 weeks can be achieved.

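### Section 11.6.1 names only crude subject counts for adverse events, so later-onset or continuing-hazard events would read lower at an early registration snapshot than at study end

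*Combined protocol and SAP*

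**What the plan says.** Long-term safety is the primary endpoint, and TEAEs are its first listed component (Section 3.1.3).

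- **Measure.** Section 11.6.1: "The frequency of subjects experiencing a specific TEAE will be tabulated by system organ class, preferred term, seriousness", and also by worst severity and relationship to study drug. A subject counts once per event. Adverse events of special interest (AESIs) are summarized separately. Deaths, serious adverse events (SAEs) and events leading to discontinuation are listed.
- **Population.** Section 11.1: "The safety analysis set will include all subjects who received at least 1 dose of study medication".
- **Snapshot.** Section 11.8 expects that "approximately 500 subjects across the development program for DS-5565 will need to be exposed to DS-5565 for at least 52 weeks". If this study "is still ongoing when the above condition is met, the sponsor intends to take a snapshot of the database", that snapshot supports registration. No adverse event measure is named for it.
- **Other sources of one-year subjects.** Section 1.2: "DS-5565 is an oral analgesic drug being developed for chronic use in FM and other indications".
- **Withdrawals.** Section 4.2.3: "Subjects removed from the study for any reason will not be replaced".
- **Later SAP.** Section 11.2: "A detailed SAP describing the methodology to be used in the final analysis will be prepared before data unblinding".
- **Event window.** Section 9.1 collects adverse events until 4 weeks after the last dose. Section 11.6.1 ties a TEAE to emergence on treatment, or to worsening from the pre-treatment state, and gives no end date. Section 9.10.2 has withdrawal symptoms, rated after dosing has stopped, reported as a TEAE.

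**The concern.** Follow-up will be unequal. Some subjects withdraw, and adverse events can themselves lead to discontinuation (Sections 3.1.6.1 and 5.1.1). At a snapshot, others have simply not yet reached Week 52. A crude percentage counts a subject dosed for five weeks the same as one dosed for a year. For an event that keeps occurring over time, the percentage therefore depends on when the database is cut.

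Laboratory values, vital signs and the C-SSRS are summarized by assessment or visit (Sections 11.6.2, 11.6.3 and 11.6.6), so the missing time dimension concerns adverse events. At stake is how the registration tables are read: the same drug and the same underlying risk could give a lower figure at the snapshot than in the final report.

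**Working it through.** **What can be reproduced.** The target of 500 has no formula, event rate or dropout figure behind it. The only checkable arithmetic is the duration: 52 + 4 = 56 weeks for rollover subjects and 56 + 3 = 59 for de novo subjects. Both agree with Section 3.1.5.

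**Inputs.** From the documents: 52 weeks of treatment, 4 weeks of follow-up, a program target of 500, and a study length of about 39 months (Section 3.1.4). Assumed, because the documents give no figure:

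- true 52-week risk 10%, constant hazard: λ = −ln(0.9)/52 = 0.002026 per week
- completion 80% or 50%, constant withdrawal hazard: μ = −ln(completion)/52 = 0.004291 or 0.013330 per week
- entry just large enough for 500 completers: N = 500/0.8 = 625 or 500/0.5 = 1000
- even entry over A = 52 weeks, or about 110.5 weeks (39 months is 169.6 weeks; less 59)
- k of the program's 500 coming from this study: 250, 400 or 500

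**Formula.** The snapshot falls at T = 52 + A × k/500. A subject with potential treatment time c = min(52, T − entry) contributes λ/(λ+μ) × (1 − exp(−(λ+μ)c)), averaged over subjects entered by T. At study end c = 52 for everyone, and the result equals the 52-week cumulative incidence with withdrawal as a competing event.

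**Study end.**

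- 80% completion: 0.32073 × (1 − 0.9 × 0.8) = 0.32073 × 0.28 = 8.98%
- 50% completion: 0.13195 × (1 − 0.9 × 0.5) = 0.13195 × 0.55 = 7.26%

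**One snapshot in full** (80% completion, k = 250, A = 110.5). T = 52 + 55.25 = 107.25 weeks. A share 55.25/107.25 = 0.515 could have had 52 weeks and contributes 8.98%. The other 0.485 has c spread evenly over 0 to 52 and contributes 0.32073 × (1 − 0.28/0.3285) = 4.74%. Total: 0.515 × 8.98 + 0.485 × 4.74 = 6.92%.

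| Completion | k | Snapshot crude % (A = 110.5 to A = 52) | Study end % | Gap, points |
|---|---|---|---|---|
| 80% | 250 | 6.92 to 7.98 | 8.98 | 1.0 to 2.1 |
| 80% | 400 | 8.64 to 8.83 | 8.98 | 0.2 to 0.3 |
| 80% | 500 | 8.98 | 8.98 | 0 |
| 50% | 250 | 5.73 to 6.58 | 7.26 | 0.7 to 1.5 |
| 50% | 400 | 7.03 to 7.16 | 7.26 | 0.1 to 0.2 |
| 50% | 500 | 7.26 | 7.26 | 0 |

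The zero at k = 500 depends on entry being no larger than needed. With an assumed 2000 entrants, 40% withdrawal and all 500 from this study, the snapshot gives 6.0% to 6.8% against 7.9% at study end.

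**Early-onset events** (10% risk confined to weeks 0 to 4). Study end is 9.92% and 9.74% at 80% and 50% completion. The lowest snapshot figures are 9.73% and 9.57%.

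**Person-time rate.** At study end with 80% completion, 56.1 events in 532.7 patient-years give 10.54 per 100 patient-years (95% CI about 7.9 to 13.7 on 56 events). In the worked snapshot, 42.0 events in 398.6 patient-years give the same 10.54.

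**Window.** If events in the 4 weeks after the last dose count at the same hazard, study end becomes 9.7% and 8.0%. If those events enter the numerator while person-time stops at the last dose, the rate is inflated to 60.7/532.7 = 11.4 and 80.1/688.8 = 11.6. The window therefore has to match on both sides.

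**The case against.** The strongest objection is that the omission is not proven. The protocol defers detail to a SAP that was not supplied, and rates, exposure tables and a TEAE end date are normal SAP content. That stands: this is a gap in the protocol text, not evidence that the analyses will be absent. It is not a full answer, because that SAP is promised for the final analysis and timed to unblinding in a study without blinding (Section 5.1.1). Nothing ties it to the snapshot.

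Second, the size rests on assumptions. The snapshot is conditional, and Section 11.11 sets this study's own goal as to "collect long-term safety data on approximately 500 subjects exposed to DS-5565 for at least 52 weeks", which is the no-gap case in the table. That also stands. Other indications make a smaller share possible, but no split is given.

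Third, the study is single-arm and descriptive. No between-arm comparison is biased, and nothing in the plan presents the crude percentage as an estimate of 52-week risk. This is correct.

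A reader might infer three stronger things that the documents do not support:

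- **That the final tables understate risk.** With withdrawal as a competing event there is no shortfall at study end. Against the 10% figure there is one only if withdrawal is treated as non-informative censoring.
- **That the adverse event window is open.** The collection period is settled in Section 9.1. Only the TEAE status of events starting after the last dose is unclear.
- **That the labels by treatment (Section 11.6.2) and by treatment arm (Section 11.6.4) have no possible meaning.** Section 3.2.1.1 uses arm for a dose. These labels, the ECG grouping and any split by dose at onset are minor clarifications outside this point.

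**Conclusion.** The point holds as a cheap improvement. For later-onset or continuing-hazard events, crude percentages at a snapshot taken while subjects are still on treatment will be below the study-end figures, and the two should not be compared without allowing for exposure. The documents establish that direction and no size.

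Under the assumed 10% constant-hazard risk, 50% to 80% completion and entry over 52 to 110.5 weeks, the on-treatment gap is 0.7 to 2.1 points if this study supplies 250 of the 500, 0.1 to 0.3 at 400 and zero at 500 when entry is just sufficient. For events confined to the first weeks it is at most about 0.2 points. Separately, and with no assumption needed, Sections 9.1, 9.10.2 and 11.6.1 leave the TEAE status of other post-dose events unstated.

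**What to change.** Keep the crude table. For common TEAEs, SAEs and AESIs, specify at both the snapshot and the final analysis:

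1. An exposure summary and incidence per 100 patient-years with a 95% CI, using the same window for numerator and person-time.
2. Cumulative incidence to Week 52, censored administratively at the data cut-off, with withdrawal as a competing event. Add an analysis that censors at withdrawal as sensitivity, because withdrawal can follow from an adverse event.

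Reconcile Section 11.6.1 with Sections 9.1 and 9.10.2 by stating whether adverse events that start in the 4 weeks after the last dose count as TEAEs. State that the SAP covers the snapshot and is final before the snapshot is taken.

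The cost is SAP wording and programming; onset, dosing and withdrawal dates are already collected. The downside is more tables and possibly less favourable reported 52-week risks. The patient-year rate is the same at every cut only if the hazard is roughly constant, which is why the cumulative incidence should stand beside it.
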